4.3 An overview of analytic methods and assumptions in calculations of statistical power. For statistical methods, most of the outcomes and hypotheses we expect to collect and test can be analyzed using standard approaches of survival analysis, generalized linear models (i.e. logistic regression, Poisson regression, negative binomial regression), generalized estimating equations (GEE) models for binary data, and mixed-effects models for continuous data.

In the sections below, we will describe some specific analysis plans for outcomes addressing our primary aims (total mortality, health care costs) and for a number of the outcomes addressing our secondary aims (frailty, diabetic microvascular complications, and quality of life). We will also describe our approach to supporting analyses, exploration of possible mechanisms for observed effects, our tertiary aim, and to identification of effect modification or subgroup effects.

Many of the outcomes we will analyze will be defined by the incidence of an event. The main comparisons of intervention groups with respect to the distribution of time until the first post-randomization occurrence of an event will be based on survival analyses. This approach is useful in that it allows for varying lengths of follow-up among participants and for comparisons to be made over the entire course of the follow-up period. To compare intervention arms, we will use a Mantel-Haenszel test with unit weighting, stratified by clinical center. This test is equivalent to a log-rank test and, if the proportional hazards assumption is warranted, to a Cox proportional hazards model. To incorporate covariates into survival models, proportional hazards models will be used. The proportional hazards assumption for the intervention effect will be assessed by examining Schoenfeld residuals plotted against time and by including covariate by time interactions in the model. Outcomes subject to competing risks for which loss-to-follow-up for one time-to-event endpoint may be a result of death or other competing risks [Putter, 2007; Byersman, 2012] will be analyzed using the flexible approach described in Scheike and Zhang [Sheike, 2008] implemented in the R `timereg` package [Sheike, 2011] which generalizes the approach of Fine and Gray [Fine, 1999] for directly modeling the cause-specific subdistribution hazard function.

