5.0 Analytical Plan For Specific Aims

5.1 Specific Aim 1 (primary) is to test the hypothesis: The hazard rates for total mortality will differ between intervention groups across follow-up. Mortality will be adjudicated from death certificates, recent hospitalization records (discharge summaries only), outcomes interviews, and National Death Index (NDI) search. All data collected since randomization will be included. Time to death from any cause will be measured from the time of randomization. Follow-up time for participants who remain event free will be calculated as the time in years from randomization to their last available visit. The primary analysis of the all-cause mortality will be proportional hazards regression with stratification for clinical sites, mirroring the analysis of the trial's primary composite cardiovascular disease outcome. Significance for the intervention effect will be based on the likelihood ratio test. Hazard ratio (HR) and 95% confidence intervals will be constructed from the fitted models. The proportional hazard assumption will be examined using log/log plots of survival [e.g. Lagakos, 1984] and alternative models may be used as sensitivity analyses, if necessary. For example, we have experience in applying parametric Weibull models [Lawless, 2003] to the LA mortality data. In addition, Kaplan-Meier plots will be used to present the survival curves by intervention.

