Power: If 3800 participants are enrolled in LA-E and 8% in the DSE group will be classified as frail during LA-E, we project 80% power to detect an odds ratio of 0.70 (two-sided 0.05 type 1 error). Note that our preliminary data with a somewhat limited definition of frailty provide support for these assumptions: observed OR=0.75 [95% CI 0.57, 0.98] and 6.4% prevalence in the DSE group.

As noted earlier, LA-E plans to follow 3,800 participants through 2020, with collection of MMD data on two occasions, 2 years apart. If we assume 12.7% of the DSE group experience PMMD, a two-sided 0.05 probability of Type I error, and 1900 active participants in each group are followed for MMD, LA-E will have approximately 80% power to detect a 25% reduction in the

odds of PMMD in the ILI group compared to the DSE group. This percent relative reduction is consistent with what was observed in the LIFE [Pahor, 2014] trial (physical activity vs successful aging interventions) where the physical activity group had a 28% reduction in the hazard rate for PMMD.

5.4 Specific Aim 4 (secondary) is to test the hypothesis: the time until first occurrence of end stage renal disease (RRT or death from nephropathy) post-randomization will differ between intervention groups.

The primary outcome for diabetic nephropathy will be the first occurrence of **end stage renal disease (ESRD)**, defined as renal replacement therapy (RRT) or death from nephropathy. Information on outpatient and inpatient dialysis has been a crucial part of data collection since the beginning of the LA trial and has been collected every 6 months throughout. Renal transplants have been captured throughout follow-up, as well. This will continue in LA-E. The distribution of time to first occurrence of ESRD will be compared between ILI and DSE using survival analyses as described for total mortality (Section 5.1). Because data on ESRD will continue to be collected every six months in LA-E (as it was in LA and LA-C), censoring and follow-up times will cluster around these six month time points even though we will use the dates of the participant encounter to calculate follow-up time. Because 6-month intervals are fairly short and regular in length throughout follow-up, we will follow the commonly accepted recommendations [Leung, 1997] and will not complicate the analysis by considering interval censoring. All data since randomization will be used for analysis.

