Supporting analyses include other measures of diabetic nephropathy and neuropathy and sensitivity analyses accounting for competing risk of death.

Supporting outcomes related to diabetic nephropathy will be derived from serum creatinine. Serum creatinine was collected annually from baseline to year 4 and biannually thereafter in LA and LA-C. **Estimated Glomerular filtration rate (eGFR)** will be calculated based on CKD-Epi equation [Levey, 2009]. Renal outcomes for supporting analyses will be the **doubling of serum creatinine from baseline** and **serum creatinine ≥ 2.5 mg/dl**. These will be analyzed as time until first occurrence of an event. Because death censors the occurrence of renal events, we will conduct a sensitivity analysis to examine these renal outcomes (including ESRD) accounting for the competing risk of death. We will create an indicator variable to distinguish between three different states: participants who experienced a particular renal event, participants who died before experiencing a particular renal event, and participants who were censored at their last available follow-up visit. We will fit a Cox model to estimate type-specific hazard ratio treating the participants who died without experiencing a particular event as censored. Alternatively, we will model the cumulative incidence function and estimate the subdistribution hazard ratio. The cumulative incidence function will be plotted for DSE and ILI.

We will also compare the average level of eGFR over time between DSE and ILI using linear mixed effects models. The basic model will include an indicator variable for intervention assignment, follow-up time, and the interaction between the intervention and follow-up time while adjusting for clinic centers and baseline eGFR. Least square means will be plotted to portray the trend over time. The average post-randomization levels of the overall eGFR for DSE and ILI will be estimated and compared using linear contrasts. The difference in average score between DSE and ILI at a particular visit will also be compared using linear contrasts. The covariance between repeated measures will first be characterized with an unstructured

covariance structure. If the model does not converge, we will explore simpler covariance structures such as compound symmetry. Akaike information criterion (AIC) will be used to aid in selection of an appropriate covariance structure.

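### The ESRD and creatinine ≥2.5 mg/dl time-to-event tests in SAP 5.4 do not adjust for baseline eGFR; they are valid but give up some efficiency

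*Combined protocol and SAP*

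**What the plan says.** For the endpoint that decides Aim 4, SAP Section 5.4 states that "time to first occurrence of ESRD will be compared between ILI and DSE using survival analyses as described for total mortality (Section 5.1"). Section 5.1 reads: "The primary analysis of the all-cause mortality will be proportional hazards regression with stratification for clinical sites", with a likelihood ratio test for the intervention effect.

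SAP Section 4.3 gives the general rule for event outcomes: "we will use a Mantel-Haenszel test with unit weighting, stratified by clinical center". It adds: "To incorporate covariates into survival models, proportional hazards models will be used". It names no covariate for any renal event.

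For the supporting endpoints, creatinine doubling from baseline and creatinine ≥2.5 mg/dl, Section 5.4 says only: "These will be analyzed as time until first occurrence of an event". The competing-risk sensitivity analyses in that section name no kidney covariate either.

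The baseline value exists: "Serum creatinine was collected annually from baseline to year 4". The repeated-measures eGFR model in the same section includes "the interaction between the intervention and follow-up time while adjusting for clinic centers and baseline eGFR", and the neuropathy questionnaire model includes its own baseline status.

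The power paragraph of Section 5.4 claims 80% conditional power for an 18% reduction in ESRD, using two-sided log-rank tests and a boundary of 2.1. It says power is slightly greater at 1.96.

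**The concern.** Kidney function at entry is a natural candidate for a strong predictor of later ESRD. For the ≥2.5 mg/dl endpoint, it also sets how far each person starts from the threshold. In a proportional hazards model, leaving out a strong predictor makes the expected hazard ratio lie closer to 1 than the ratio conditional on that predictor, and the test has less power than the adjusted one. Any chance difference between arms in baseline kidney function also stays in the estimate.

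The SAP collects the variable and uses it in a supporting model, but not in the test that carries the aim. Because covariates are allowed in general and none is named here, adjustment could also end up being decided after results are seen.

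**Working it through.** **Inputs from the documents.** 5,145 randomized 1:1 within center; hazard ratio 0.82 (an 18% reduction); boundary 2.1; 80% conditional power; all data since randomization. **Not in the documents:** ESRD event count, interim z, information fraction, and the ESRD hazard ratio per SD of lower baseline eGFR. The last is therefore varied from 1.5 to 4.5, and control-arm ESRD incidence from 2% to 10%.

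**Step 1: the stated 80%.** It cannot be reproduced, because the conditional inputs are missing. Treated as unconditional, events = 4(c + 0.8416)² / (ln 0.82)².
- c = 2.1: 4 × 2.9416² / 0.19845² = 879 events, or 879/5,145 = 17% of the cohort.
- c = 1.96: 4 × 2.8016² / 0.19845² = 797 before rounding up.
- With 879 events, power at 1.96 is 83.7%, which fits the SAP's remark that it is slightly greater.

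As conditional power, far fewer events could suffice if the interim z is already large: at information fraction 0.5, about 349 events in total at z = 2.5, or 208 at z = 2.8. So 879 is not implied by the SAP.

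**Step 2: efficiency.** Let r be the large-sample log hazard ratio with eGFR omitted, divided by ln 0.82. The calculation assumes a normal covariate, Weibull event times and 25% competing death.
- If the adjusted test has 80% power, the unadjusted test has Φ(2.9416r − 2.1).
- If the unadjusted test has 80%, as the SAP states, the adjusted test has Φ(2.9416/r − 2.1).

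Example (4% incidence, 3 per SD): r = 0.9593. Then 2.9416 × 0.9593 − 2.1 = 0.722, giving 76.5%; and 2.9416/0.9593 − 2.1 = 0.966, giving 83.3%.

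| Incidence | HR per SD | HR, eGFR omitted | r | Unadjusted power if adjusted = 80% | Adjusted power if unadjusted = 80% |
|---|---|---|---|---|---|
| 2% | 1.5 | 0.820 | 0.998 | 79.9% | 80.2% |
| 2% | 2 | 0.821 | 0.994 | 79.5% | 80.5% |
| 2% | 3 | 0.824 | 0.978 | 78.2% | 81.8% |
| 2% | 4.5 | 0.829 | 0.943 | 75.0% | 84.6% |
| 4% | 1.5 | 0.821 | 0.996 | 79.7% | 80.3% |
| 4% | 2 | 0.822 | 0.988 | 79.0% | 81.0% |
| 4% | 3 | 0.827 | 0.959 | 76.5% | 83.3% |
| 4% | 4.5 | 0.836 | 0.906 | 71.4% | 87.5% |
| 10% | 1.5 | 0.822 | 0.991 | 79.2% | 80.8% |
| 10% | 2 | 0.825 | 0.970 | 77.4% | 82.5% |
| 10% | 3 | 0.834 | 0.913 | 72.1% | 86.9% |
| 10% | 4.5 | 0.848 | 0.832 | 63.6% | 92.5% |

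**Step 3: simulation check** (N = 5,145, 600 trials per scenario, boundary 2.1, no clinic strata; Monte Carlo error up to about 2 points).

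| Incidence | HR per SD | True HR | Power unadjusted | Power adjusted |
|---|---|---|---|---|
| 4% | 2 | 0.66 | 72.0% | 72.8% |
| 4% | 4.5 | 0.66 | 61.7% | 72.3% |
| 10% | 3 | 0.76 | 72.5% | 81.3% |
| 4% | 3 | 0.82 | 18.8% | 20.0% |
| 4% | 3 | 1.00 (null) | 2.0% | 2.3% |

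Under the null, neither test exceeds the nominal 3.6%. The fourth row has about 191 events. It shows that the gain in points is small when power is low to begin with.

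**Step 4: chance imbalance.** The SE of the between-arm difference in a standardized covariate is √(4/5,145) = 0.028 SD. At 3 per SD, a 1.96-SE imbalance shifts the log hazard ratio by 1.96 × 0.028 × ln 3 = 0.06, a factor of about 1.06, so 0.82 could read 0.77 to 0.87. By comparison, the SE of the log hazard ratio at 191 events is about 2/√191 = 0.145.

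**The case against.** The strongest reply is that nothing is wrong with the planned test. In a cohort randomized 1:1, a clinic-stratified comparison is valid. Section 5.1 chose that model deliberately, to mirror the original cardiovascular analysis, and Section 5.4 extends it to ESRD. All of this stands. A reader might infer that the planned hazard ratio is biased toward the null. It lies closer to 1 only relative to an eGFR-conditional ratio, which the SAP does not name as its target.

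A reader might also infer that the study falls short of its stated power, or that at least 5 points are lost under its own target. Neither follows. The 80% is for log-rank tests, so adjustment would add to it. Large losses appear when about 880 ESRD events are assumed, and a conditional power statement does not imply that number. It is also a poor anchor: SAP Section 5.2's neighbor for mortality, Section 5.1, projects 509 deaths in the DSE arm, so with no more deaths in ILI, 879 ESRD cases would equal at least 879/1,018 = 86% of all deaths.

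The charge of internal inconsistency is weak. Baseline eGFR enters a model whose outcome is eGFR itself, whereas ESRD has no baseline value. Chance imbalance is modest at this sample size, and the ordinary confidence interval already allows for it.

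Changing the lead model when data have been accruing since randomization is a mid-course change. That calls for care over timing. It is met by fixing the covariate before any further unblinded comparison and showing both models.

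What survives is narrower: a baseline measure already in hand is left unused, and adjustment lost no power in any scenario run.

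**Conclusion.** The point holds as a matter of efficiency on a secondary aim. It is not an error in the test or in the stated power.

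For a test near 80% power, the cost of leaving out baseline eGFR is:
- about 1 point or less at 2–4% incidence with a hazard ratio per SD up to 2;
- about 2 to 9 points at 2–4% incidence with 3 to 4.5 per SD (about 2 to 7.5 if the unadjusted test is the one set at 80%);
- more only if ESRD is common: at 10% incidence with 3 to 4.5 per SD, about 8 to 16 points (about 7 to 12.5 with the unadjusted test set at 80%).

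Incidence and prognostic strength are both assumptions, and the table treats power as unconditional. If ESRD events are few and actual power is low, the gain is about 1 point, as in the 191-event simulation.

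The figures were computed for a generic time-to-event endpoint such as ESRD. They are only indicative for creatinine ≥2.5 mg/dl. A reader might extend them to creatinine doubling, but its definition already contains the baseline value and no ratio endpoint was examined, so no such gain should be claimed.

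**What to change.** In SAP Section 5.4, before any further unblinded comparison:
- State that the ESRD and creatinine ≥2.5 mg/dl analyses are proportional hazards models stratified by clinic and adjusted for continuous baseline CKD-Epi eGFR.
- Prespecify the functional form (linear, or a stated spline) and a simple rule for missing baseline values.
- Base the likelihood ratio test on that model, say that its hazard ratio is conditional on baseline eGFR, and report the clinic-only model as supporting.
- Leave creatinine doubling out of this change.

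No new data are needed. The costs are a conditional rather than marginal hazard ratio in the lead analysis, and a power paragraph that would then describe the supporting unadjusted test and should say so. Adding the ESRD event count and interim statistic behind the 80% would let readers judge which row of the range applies.

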Supporting analyses will focus on nephropathy derived from serum creatinine (i.e., doubling of serum creatinine since randomization or serum creatinine exceeding ≥ 2.5 mg/dl, both representing high risk of need for RRT or death from renal failure. Supporting analysis will also include a neuropathy outcome assessed by the Michigan Neuropathy Screening Instrument (MNSI), comprised of a self-report history questionnaire; a foot inspection for evidence of excessively dry skin, callous formation, fissures, and frank ulceration or deformities; vibration sensation; ; and monofilament testing for touch sensitivity (Feldman, 1994). We will also continue to obtain self-reported information on the diagnosis of diabetic retinopathy, amputations, laser treatment, and cataract extraction.

Quality of life will be measured by the Medical Outcomes Study Short Form 36 (SF-36), which assesses health across eight domains: physical functioning; role limitations because of physical health problems; bodily pain; social functioning; general mental health (psychological distress and psychological well-being); role limitations because of emotional problems; vitality (energy/fatigue); and general health perceptions (Ware, 1992).

Supporting analyses will include the individual domains of the SF-36, the SF-6D, late life depression assessed by the Patient Health Questionnaire (PHQ-9) (Kroenke, 2001); healthy non-disabled life-years estimated using the SF-36 and mortality data; and the EuroQual Feeling Thermometer (The EuroQual Group, 1990), the Loneliness Questionnaire (Hughes 2004; Russell 1996), the Resilience Questionnaire (Smith, 2008), and the Pittsburgh Fatigability Scale for Older Adults (Glynn, 2015).

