1.4.4 Schedule for Ascertaining Outcomes

Study measures will be obtained during the Look AHEAD Extension at clinic exams and at six month phone contacts. Participants will be invited to attend two clinic examinations at an interval of approximately two years. All clinic visits will involve a blood draw, physical and anthropometric measures, physical function measures, questionnaires, and interviews for study outcomes. In addition, the second clinic visit will include waist circumference measures and the cognitive assessment among participants who consent. Some participants will also be asked to participate in the DXA and/or accelerometry sub-study. All participants will receive six month phone calls for study outcomes. The list of study measures and frequency of collection is shown in Table 1.

1.4.5 Table 1. Study Measures and Time Points for Data Collection in the Look AHEAD Extension

Table 1. Study measures and time points for data collection in the Look AHEAD Extension			
	EXAM 1 (2016- 2018)	EXAM 2 (2018- 2020)	SIX MONTH PHONE CALLS
Laboratory Measures			
HbA1c	X	X	
Serum Creatinine	X	X	
Stored Plasma, Serum and Whole Blood	X	X	
Physical Measures			
Seated BP & Pulse	X	X	
Weight, Height	X	X	
Waist Circumference		X	
Foot exam for neuropathy	X	X	
Outcomes/Events Interview			
Hospitalizations (& discharge summaries)	X	X	X
Outpatient Visits	X	X	X
Major Health Events	X	X	X
Falls	X	X	X
Renal Replacement Therapy	X	X	X
Amputations	X	X	X
Mortality (death certificates and other records)	X	X	X
Questionnaires			
Participant Contact Form & Proxy Identification	X	X	X
Michigan Neuropathy Screening Instrument	X	X	
Medications	X	X	
SF-36	X	X	
PHQ-9	X	X	
EuroQual (Feeling) Thermometer	X	X	
Loneliness Questionnaire	X		
Paffenbarger Physical Activity	X	X	
Falls Efficacy Scale International	X	X	
Resilience Questionnaire	X		
Pittsburgh Fatigability Scale	X		
Pepper Assessment Tool for Disability (PAT-D)	X	X	
Physical Function and Abilities Questionnaire	X	X	
Sleep Questionnaire	X	X	
Cognitive Function Battery			
Interviewer Administered Battery (45 min)		X	
Digit Symbol Coding Test		X	
Rey Auditory Verbal Learning Test		X	
Modified MiniMental State Exam		X	

Trails Making Test Parts A&B		X	
Modified Stroop Color-Word Test		X	
Functional Assessment Questionnaire (as needed)		X	
Dementia Questionnaire (as needed)		X	
Physical Function			
400-m Walk/alternate 4 meter walk	X	X	
Grip Strength	X	X	
Short Physical Performance Battery (SPPB)	X	X	
Sub studies			

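### The supporting creatinine endpoints do not count renal replacement therapy or death from nephropathy, so some ESRD cases can be non-events on the milder endpoint

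*Combined protocol and SAP*

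**What the plan says.** SAP section 5.4 makes ESRD (RRT or death from nephropathy) the principal outcome of Aim 4. It then adds kidney endpoints from one source: "Supporting outcomes related to diabetic nephropathy will be derived from serum creatinine". These are "doubling of serum creatinine from baseline" and a creatinine of at least 2.5 mg/dl, each analysed as time to first occurrence. Protocol section 1.4.2 describes the two thresholds as "both representing high risk of need for RRT or death from renal failure".

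For the earlier phases, SAP 5.4 says: "Serum creatinine was collected annually from baseline to year 4 and biannually thereafter in LA and LA-C". For the Extension, protocol section 1.4.4 says: "Participants will be invited to attend two clinic examinations at an interval of approximately two years". Protocol Table 1 marks creatinine at both exams and not at the six-month calls, and SAP Exhibit 1 lists it at the biennial exams. Table 1 marks RRT at both exams and at every six-month call.

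The sensitivity analysis for the competing risk of death sorts participants into those with the renal event, "participants who died before experiencing a particular renal event, and participants who were censored at their last available follow-up visit". Its Cox model censors deaths without the event; a cumulative-incidence model with a subdistribution hazard ratio is the alternative.

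The reason for ignoring interval censoring is given in the ESRD paragraph: "Because 6-month intervals are fairly short and regular in length throughout follow-up". Nothing equivalent is said for creatinine. No rule covers creatinine or eGFR values obtained after dialysis or transplant.

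**The concern.** The supporting endpoints are meant to show an earlier stage of the process that ends in ESRD. A participant on RRT has, by the protocol's own description, reached what the thresholds are meant to predict. Yet RRT has no place in the definition of the creatinine endpoints or in the three-state variable. If no qualifying creatinine is on file, that participant contributes a non-event.

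Such censoring is informative, because it depends on how fast kidney function is lost and on whether the participant reaches the next draw. A disagreement between ESRD and the creatinine endpoints could then reflect the definition and not the intervention.

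Two related gaps matter. First, values drawn after dialysis or transplant reflect the treatment, and they would enter the eGFR mixed model; a transplant would look like recovery. Second, with draws about two years apart, the date of a threshold crossing is known only to within that gap.

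**Working it through.** **1. Schedules side by side.**

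| Phase | Creatinine | RRT |
|---|---|---|
| Baseline to year 4 | annual | every 6 months |
| After year 4, through LA-C | stated as *biannually* | every 6 months |
| Extension | Exam 1 (2016-2018), Exam 2 (2018-2020) | both exams and every 6 months |
| After Exam 2 to 7/2020 | none | every 6 months |

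Read literally, *biannually* means twice a year. That does not fit the single planned clinic visit of LA-C (protocol section 1.1) or the biennial exams of the Extension. Every two years is the likely meaning, but the text must be reconciled.

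**2. How each course is scored.** All rows assume that the threshold is crossed after the last non-qualifying draw.

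| Course | Creatinine endpoint | ESRD |
|---|---|---|
| RRT, then a qualifying draw | event, dated late | event |
| RRT, no later qualifying draw | censored | event |
| Death from nephropathy before a qualifying draw | censored in the Cox model; competing death in the subdistribution model | event |

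The second and third rows are the problem. They follow from the definitions and need no numerical assumption.

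**3. Scale.** The plan states no event count or power for the creatinine endpoints, so there is no figure to reproduce. The two illustrations below rest on assumed progression.

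*Model A (linear decline).* Assume doubling at half the baseline eGFR and RRT at eGFR 10; both are modelling assumptions only. The window from doubling to RRT is (baseline/2 - 10)/rate. With draws L years apart, the share of ESRD cases with no doubling recorded before RRT is max(0, 1 - window/L). For L = 2:

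| Decline (ml/min/yr) | Baseline 80: window, share | Baseline 60: window, share |
|---|---|---|
| 5 | 30/5 = 6 y, 0% | 20/5 = 4 y, 0% |
| 10 | 30/10 = 3 y, 0% | 20/10 = 2 y, 0% |
| 20 | 30/20 = 1.5 y, 25% | 20/20 = 1 y, 50% |
| 30 | 30/30 = 1 y, 50% | 20/30 = 0.67 y, 67% |

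*Model B (exponential).* Assume that crossing is uniform within the interval L and that the time from crossing to RRT or death is exponential with mean m. The share of crossers who reach RRT or death before the next draw is 1 - (m/L)(1 - exp(-L/m)). For example, L = 2 and m = 1 give 1 - 0.5 x (1 - 0.135) = 57%.

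| L | m = 1 y | m = 2 y | m = 3 y | m = 5 y |
|---|---|---|---|---|
| 2 y | 57% | 37% | 27% | 18% |
| 1 y | 37% | 21% | 15% | 9% |

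Both models give upper bounds on lost events, because they treat every case that reaches RRT before the next draw as never recorded. If half of the L = 2 cases in Model B still qualify at a later draw, the range over m = 1 to 5 falls to 28%-9%. If 80% do, it falls to 11%-4%.

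**4. Interval censoring.** The stated justification rests on six-month contacts. The Extension creatinine interval is about two years, roughly four times as long, so the justification does not carry over.

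**The case against.** A reader might infer that all creatinine data come from draws two years apart and that the fastest progressors are necessarily scored as event-free. The documents do not support that.

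- Draws were annual to year 4, and the two-year gap is explicit only for the Extension.
- The three-state rule belongs to a sensitivity analysis in which death has its own state. It is not the main endpoint rule, although the main analysis adds no RRT rule either.
- A dialysis patient who attends a later exam may still qualify, so the event can be late instead of lost.
- Whether event-free time runs on after dialysis depends on whether a follow-up visit includes a telephone contact. If only clinic visits count, a participant who starts RRT after Exam 2 is censored at Exam 2 and no later time is credited.
- Model A gives no loss at 10 ml/min/yr or slower with two-year draws, and the documents do not say how often faster decline occurs.

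A reader might also take the excess of about 40 deaths in DSE (SAP section 4.2) as evidence of bias between arms. Those deaths are all-cause, nothing ties them to kidney disease, and the draw schedule is the same in both arms.

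Finally, it is defensible to keep the thresholds as pure laboratory markers, since composites overlap with the ESRD outcome they support.

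These points limit the size and certainty of the problem. They do not remove the two scoring paths that turn an ESRD case into a non-event, nor the silence on values after RRT.

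**Conclusion.** The point holds as a weakness of the supporting renal analyses and should be corrected. Neither creatinine endpoint counts RRT or death from nephropathy, and in the Extension both depend on two draws about two years apart. Some ESRD cases can therefore be censored, or treated as competing deaths, on the milder endpoint.

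The size is unknown. The illustrations run from no loss to large losses, depending wholly on assumed progression and on how many cases qualify at a later draw. The direction between arms is not established. The effect on eGFR means cannot be estimated, because the documents give no counts of RRT or transplant.

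It would be wrong to conclude that the Aim 4 result is compromised. ESRD counts RRT and death from nephropathy directly, with contacts every six months, so its test is unaffected.

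**What to change.** In SAP section 5.4:

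1. Define each creatinine endpoint as the first of the creatinine threshold, RRT, or adjudicated death from nephropathy, using the six-monthly RRT data. Keep the creatinine-only version as a sensitivity analysis.
2. Censor the creatinine component at the last creatinine draw, and say whether a follow-up visit includes a telephone contact. Apply the follow-up limit in the same way whether or not RRT occurs later.
3. Exclude creatinine and eGFR values obtained after first RRT or transplant from the eGFR mixed model. Because that exclusion is itself related to outcome, add a sensitivity analysis that assigns a fixed low eGFR after RRT.
4. Add an interval-censored sensitivity analysis for the threshold component.
5. Reconcile *biannually* with the biennial schedule.

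The cost is SAP wording and programming. RRT and cause of death are already collected, and no extra blood draw is needed. The downside is that the supporting endpoints become composites that overlap with ESRD and will differ slightly from any creatinine-only report already made; the creatinine-only sensitivity analysis keeps that comparison available.
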